2.4 Per Protocol Analysis Set

The Per Protocol Analysis Set will be a subset of the Full Analysis Set consisting of patients who do not violate the terms of the protocol (patients who do not have relevant protocol deviations (RPDs, see section 2.6.2). All decisions to exclude patients and/or data from the Full Analysis Set to form the Per Protocol Analysis Set will be made prior to un-blinding the study and agreed by the study team.

The Per Protocol Analysis Set will be used to re-analyse the primary efficacy variable (as a sensitivity analysis).

2.5 Safety Analysis Set

The safety analysis set is defined as all randomised patients who received at least one dose of study medication. Patients will be analysed according to the actual treatment received. If, at any point during the treatment period, a patient received treatment which was different from which they were randomised to, they will be included in the treatment arm which they received for the majority of the treatment period.

The Safety Analysis Set will be used to analyse all safety related variables: adverse events; serious adverse events; adverse events of special interest; discontinuation of study medication due to hypoglycaemia; clinical laboratory tests; electrocardiogram (ECG); vital signs; hypoglycaemic events.

2.6 Protocol Deviations

AstraZeneca uses ICH E3 terminology for protocol deviations, which are all important deviations related to study inclusion or exclusion criteria, conduct of the trial, patient managements or patient assessment.

2.6.1 Protocol deviation monitoring

During study conduct, protocol deviations will be closely monitored and identified from two sources:

- IMPACT monitoring These are manually entered protocol deviations identified by the CRA during study conduct.
- Programmed protocol deviations These are deviations generated by execution of programs written using the predefined deviator descriptions in the SAP and protocol.

2.6.2 Protocol deviation reporting

Protocol deviations will be reviewed in a blinded fashion by the study team prior to database lock. All decisions to exclude patients and/or data from the Full Analysis Set (to form the Per-Protocol Analysis Set) will be made prior to the unblinding of the study and agreed by the study team.

Protocol deviations that are determined to affect the primary efficacy results are deemed relevant protocol deviations (RPDs). A full list of RPDs is described in Table 5.

Table 5. List of Relevant Protocol Deviations (RPDs)

Number	RPD criteria	Exclusion level
1	Randomised patients without type 2 diabetes, or with	Complete exclusion
	corticosteroid-induced Type 2 diabetes, or with maturity onset	
	diabetes in young (MODY), or with diabetes insipidus.	
2*	Randomised patients without a central laboratory	Complete exclusion
	HbA1c obtained at the Enrolment visit (Visit 1), or with	
	central laboratory HbA1c <7.5% or >10.5% as	
	measured from sample collected either at Enrolment visit	
	(Visit 1) or at an unscheduled visit prior to visit 2	
3	Randomised patients who meet one of the following	Complete exclusion
	criteria:	
	a) received a metformin dose <1500 mg, or	
	>3000 mg during the 8 weeks prior to enrolment (Visit 1), b)	
	not treated with metformin alone at any time during the 8	
	weeks prior to enrolment (Visit 1), c) metformin dose was	
	changed during the 8 weeks prior to enrolment (Visit 1)	
4	Randomised patients who were treated with	Complete exclusion
	glucocorticoids equivalent to oral prednisolone	
	\geq 10 mg (betametasone \geq 1.2 mg, dexametasone \geq	
	1.5 mg, hydrocortisone \geq 40 mg)/day for more than	
	7 days within 30 days prior to enrolment (topical or inhaled	
	corticosteroids are allowed)	
5a	Randomised patients who took antihyperglycaemic	Partial exclusion (exclusion
	medication other than protocol required	would start from the day when

9b

addition to IP (i.e. other antihyperglycaemic medications antihyperglycaemic medicine was started after discontinuation of IP are not classed as an RPD) started) 5_b insulin is used longer than permitted by the CSP and violates Partial exclusion (exclusion would start from 8th consecutive the following situations where insulin use is allowed: For up to 14 days in total during the study and up to 7 day of insulin therapy or 15th day consecutive days if patient is unable to take oral of non-consecutive therapy, medications whichever is first). For up to 14 days in total during the study and up to 7 consecutive days if there is a documented illness or infection that requires additional therapy for maintaining glycaemic control; For up to 14 days in total during the study and up to 7 consecutive days if patients have to temporarily stop IP or metformin due to recommendations made in the clinical study protocol For up to 7 days during hospitalisation. When the reason for hospitalisation is the management of the patient's glycaemic control, treatment with insulin is considered a rescue and is allowed for as long as clinically necessary Or Partial exclusion (exclusion 5c Metformin dose was changed for patients who were randomised and still taking the double-blind study medication. would start from the date when Metformin dose was changed). 6a Patients who received incorrect investigational product at any Partial exclusion (exclusion time during the study would start from the date when the incorrect IP was taken) Randomised patients who are judged to be noncompliant in Complete exclusion 6b terms of overall compliance, i.e., who took less than 80% or more than 120% of their prescribed dose of study medication during the double-blind treatment period. 7 Randomised patients who receive no double-blind medication Partial exclusion (exclusion would start from the 14th for ≥2 consecutive weeks consecutive day the medication was not taken in an interruption) Treatment with systemic glucocorticoids equivalent to oral Partial exclusion (exclusion starts 8 prednisolone ≥ 10 mg (betamethasone ≥ 1.2 mg, from the 5th day of therapy with dexamethasone ≥1.5 mg, hydrocortisone ≥40 mg) per day for the oral steroids provided in the \geq 5 consecutive days of therapy. doses higher than equivalent to oral prednisolone). 9a* If TSH is abnormal and free T4 is missing or abnormal at visit Complete exclusion 1 or at an unscheduled visit prior to visit 2

dapagliflozin/saxagliptin or dapagliflozin or glimepiride in

other than CSP required

Complete Exclusion

TSH was not performed at visit 1 or at an unscheduled visit

prior to visit 2

10	Known condition of congenital renal glucosuria	Complete exclusion
11	Previous randomisation to treatment in the present	Complete exclusion
	study (as assessed by exclusion criteria 36)	
12*	Creatinine clearance (CrCl) of <60 mL/min or missing CrCl	Complete exclusion
	result, based on central laboratory results from Visit 1 or at an	
	unscheduled visit prior to visit 2.	
13*	C-peptide laboratory value of <1.0 ng/mL (0.33 nmol/L; 331	Complete exclusion
	pmol/L) or missing C-peptide result, based on central	
	laboratory results from Visit 1 or at unscheduled visit prior to	
	visit 2.	
14*	FPG >270 mg/dL (>15 mmol/L) or missing FPG result, based	Complete exclusion
	on central laboratory results from Visit 1 or at an unscheduled	
	visit prior to visit 2	

^{*} If a patient has an unacceptable/missing value at Visit 1 but then has an unscheduled visit prior to Visit 2 with an acceptable value, the patient will not be considered an RPD.

Patients having relevant protocol deviations will be summarised and listed (by treatment group and overall).

Protocol deviations attributed to the GCP violations will be reported in the CSR according to the following definitions:

Table 6. List of GCP violations

Number	GCP criteria	Exclusion level
1	Delay in SAE reporting	NA
2.	Delay in pregnancy reporting	NA
3,	Delay in overdose reporting	NA
4.	Incorrect ICF handling, not in accordance to the CSP	Complete exclusion

In the unlikely case that a patient did not provide signed and dated written informed consent, he/she will be excluded from all summaries.

3. PRIMARY AND SECONDARY VARIABLES

3.1 Primary efficacy variable

The primary efficacy variable is the change in HbA1c from baseline (week 0) to week 52. Its calculation is described in Section 4.5.3.

3.2 Key secondary efficacy variables

The key secondary efficacy variables are:

- 1. Proportion of patients reporting at least one episode of confirmed hypoglycaemia (symptomatic + blood glucose ≤50 mg/dL [2.8 mmol/L]), see section 4.9.6) during the double-blind treatment period
- 2. Change in total body weight from baseline to week 52
- 3. Change in FPG from baseline to week 52
- 4. Time to rescue (start of insulin or discontinuation due to lack of glycaemic control) during the 52-week double-blind treatment period. Its calculation is described in Section 4.5.6.

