1.3 Number of patients

To demonstrate non-inferiority of dapagliflozin plus metformin or dapagliflozin plus saxagliptin plus metformin to glimepiride plus metformin for changes from baseline to week 52 in HbA1c within a non-inferiority margin of 0.30% - assuming a standard deviation 1.0%, and at a 1-sided significance level of 0.025 - 290 evaluable patients will be needed in each treatment group to provide approximately 95% power (given a true difference of zero between dapagliflozin or dapagliflozin plus saxagliptin and glimepiride). The non-inferiority margin of 0.3% as well as a common standard deviation of 1.0% were selected based on information from earlier, similarly designed studies. Assuming that 5% of patients do not have a post-baseline assessment, a total of approximately 930 patients (310 patients per treatment arm) need to be randomised. Moreover, if 30% of screened patients fail to meet screening criteria, a total of 1329 patients need to be screened.

A hierarchical testing procedure will be followed to control type 1 error rate of 0.05. Dapagliflozin plus saxagliptin plus metformin will be tested for non-inferiority first. If dapagliflozin plus saxagliptin plus metformin is non-inferior to glimepiride plus metformin then dapagliflozin plus metformin will be tested for non-inferiority.

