2.3 Full Analysis Set

The Full Analysis Set will include all randomised patients who receive at least one dose of study medication and who have a non-missing baseline value and at least one post-baseline efficacy value (i.e., HbA1c, FPG, weight). Patients will be analysed according to the treatment they were originally assigned (based on the ITT principle).

The Full Analysis set will be used for addressing the non-inferiority claim for the primary efficacy objective and also for the analysis of all secondary objectives.

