For the proportions endpoints regarding glycaemic control at week 52, all available data will be used but patients rescued prior to week 52 will be treated as treatment failures (non-responders). Subjects with missing information at week 52 (e.g. HbA1c, weight) will be counted as treatment failures. For the endpoints 'the proportion of patients with at least one episode of confirmed hypoglycaemia' and 'the proportion of patients with at least one episode of hypoglycaemia (symptomatic with blood glucose ≤70mg/dL [3.9mmol/L]), if the blood glucose value is missing for a patient with hypoglycaemia, they will not be counted as having a confirmed hypoglycaemic event.

Section 4.11 provides additional information regarding handling of missing or partial dates, inclusion of values, visit windowing, and values obtained post treatment.

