4.9.6 Hypoglycaemia

Hypoglycaemic events occurring after the start of double blind study medication up to and including 4 days after the last double-blind dosing date will be considered as obtained during the double-blind treatment period and included in the summaries described below.

The proportion of patients with hypoglycaemic events and the number of hypoglycaemic events per patient will be summarised by treatment group. Hypoglycaemic events will also be categorised as follows:

• Major hypoglycaemic events: symptomatic events requiring external assistance due to severe impairment in consciousness or behaviour, with a capillary or plasma glucose

value <54 mg/dL (<3.0 mmol/L), and prompt recovery after glucose or glucagon administration

- Hypoglycaemia: Typical symptoms of hypoglycaemia accompanied by blood glucose \leq 70 mg/dL (3.9 mmol/L)
- Other episodes of hypoglycaemia: Symptoms of hypoglycaemia without a blood glucose reading or symptoms of hypoglycaemia accompanied by blood glucose >70 mg/dL (3.9 mmol/L)
- Confirmed hypoglycaemia: Typical symptoms of hypoglycaemia accompanied by blood glucose ≤50 mg/dL (2.8 mmol/L)
- Asymptomatic hypoglycaemia: An event not accompanied by typical hypoglycaemia symptoms but with measured plasma glucose \leq 70 mg/dL (\leq 3.9 mmol/L)

Hypoglycaemic events leading to discontinuation of study medication will be summarised by treatment. A summary of hypoglycaemic events over time by treatment will also be provided.

Summaries will be produced using data obtained prior to rescue medication only then repeated using all data regardless of use of rescue medication for patients in the Safety Analysis Set. A listing of patients will be produced for all hypoglycaemic events.

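### The confirmatory hypoglycaemia test omits major events with glucose above 50 and below 54 mg/dL, and drops dosed patients who have no later efficacy value

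*SAP*

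**What the plan says.** **Endpoint.** SAP 3.2 item 1 is "Proportion of patients reporting at least one episode of confirmed hypoglycaemia (symptomatic + blood glucose ≤50 mg/dL [2.8 mmol/L"). Section 4.3 repeats the threshold. Section 4.3.1 places the endpoint second in the testing order, after HbA1c non-inferiority and ahead of body weight, HbA1c superiority, FPG and time to rescue.

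**Event categories (4.9.6).**
- Confirmed: "Typical symptoms of hypoglycaemia accompanied by blood glucose ≤50 mg/dL (2.8 mmol/L").
- Major: "symptomatic events requiring external assistance due to severe impairment in consciousness or behaviour", with a glucose value below 54 mg/dL (3.0 mmol/L) and prompt recovery after glucose or glucagon.
- Other: "Symptoms of hypoglycaemia without a blood glucose reading", or symptoms with glucose above 70 mg/dL.

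**Missing glucose (4.6.2).** "if the blood glucose value is missing for a patient with hypoglycaemia, they will not be counted as having a confirmed hypoglycaemic event".

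**Population.** The Full Analysis Set (2.3) requires a dose, a baseline value and "at least one post-baseline efficacy value (i.e., HbA1c, FPG, weight"). It serves all secondary objectives. The note under Table 11, planned Table 20 and planned Figure 6 agree. Section 2.5 states: "The Safety Analysis Set will be used to analyse all safety related variables". Its list includes hypoglycaemic events, and the set is all randomised, dosed patients. On expected losses, 1.3 says: "Assuming that 5% of patients do not have a post-baseline assessment".

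**The concern.** Two features of the step 2 test do not fit what it is meant to measure.

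First, the cut-off for the more serious category (below 54 mg/dL) is higher than the cut-off for the confirmatory one (50 mg/dL or below). Part of the major category therefore lies outside the endpoint. The composite in 3.3, HbA1c below 7% (or 7.5%) without confirmed hypoglycaemia, inherits the gap.

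Second, whether a patient had an episode can be known without any later HbA1c, FPG or weight. Requiring one makes inclusion depend on something that happens after randomisation and that an episode could influence.

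Step 2 gates every later superiority test. If confirmed events turn out to be sparse, a few patients classified one way or the other could decide whether the sequence continues.

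**Working it through.** **1. The plan's own figures.** The SAP gives no rate, sample size or power for hypoglycaemia. Its HbA1c calculation (margin 0.30, SD 1.0, one-sided 0.025, 95% power) reproduces: 2 × (1.960 + 1.645)² × 1.0² / 0.30² = 288.8, so 289 against 290 stated. Power at 290 is 0.951. Allowing for 5% loss, 290 / 0.95 = 305.3, so 306 against 310 stated.

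**2. The two glucose cut-offs side by side (4.9.6).**

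| Symptomatic, assisted event, prompt recovery | Major? | Confirmed? | Event at step 2? |
|---|---|---|---|
| glucose ≤50 mg/dL | yes | yes | yes |
| glucose >50 and <54 mg/dL | yes | no | **no** |
| no reading | no (a value is required) | no (4.6.2) | no; falls under 'other' |

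The gap is 51, 52 and 53 mg/dL in whole units, or 2.9 mmol/L to one decimal place. If such an event is the patient's only one and HbA1c is below target at week 52, the patient is a success in the composite.

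**3. The definition is not worded consistently.** Sections 3.2, 4.3 and 4.9.6 keep major apart from confirmed. The bracket in 1.1.3 sets confirmed hypoglycaemia equal to a list that runs on to major and other events, so it can be read as placing major within confirmed. Section 3.3 words the same bracket as a list of components of any hypoglycaemia.

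**4. Patients outside the Full Analysis Set.** The allowance is 0.05 × 310 = 15.5 per arm. This is an upper guide: it is not restricted to dosed patients, still less to those with an episode. Table 1 has a visit at week 2, and its notes require early-termination procedures for all who leave. That column includes weight, HbA1c and FPG, and any one of them keeps the patient in the set. The baseline condition excludes few, because 4.5.1 accepts the last value on or before the first dose.

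**5. Can a few patients matter?** The counts below are assumed, with 290 per arm and Fisher's exact test, which 4.5.7 prescribes when any arm has fewer than 5 responders. Entries are two-sided p-values after adding omitted patients.

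| Patients with an event (glimepiride vs test) | none added | +1 / +1 | +2 / 0 | 0 / +2 |
|---|---|---|---|---|
| 10 vs 2 | 0.037 | 0.054 | 0.012 | 0.174 |
| 20 vs 4 | 0.001 | 0.002 | 0.0004 | 0.008 |

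With sparse events the result can cross 0.05 in either direction. At 20 vs 4 it stayed below 0.02 in every case tried; the largest was 0.0165, with three added to the test arm. Raising the denominator from 290 to 310 with the counts at 10 vs 2 moves p only from 0.0366 to 0.0368. Restored patients therefore matter only if they bring events.

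**The case against.** **Major events are reported elsewhere.** This stands. They count in the any-hypoglycaemia endpoint (3.3), are summarised in all dosed patients before and regardless of rescue (4.9.6), and enter the adverse event tables when serious (4.9). Those results are descriptive or carry nominal p-values, so the gap concerns only the error-controlled test and the composite.

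**Two analysis sets are deliberate.** This also stands: 2.3 covers secondary objectives and 2.5 covers descriptive safety summaries. It explains the arrangement but gives no reason for an event endpoint to require a later efficacy value.

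**Requiring a glucose value for a 'confirmed' event is coherent.** It is, and 4.6.2 says so openly.

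A reader might infer more than the SAP supports:
- *Dosed patients outside the Full Analysis Set are scored as hypoglycaemia-free.* They are not; they leave numerator and denominator alike.
- *An assisted event without a reading is a major event that the test misses.* Under 4.9.6 it is not major, because that category requires a value below 54 mg/dL.
- *A sizeable share of glimepiride events is lost.* That needs event rates among excluded patients, which the SAP does not give, and early-termination visits make large losses unlikely.
- *The omissions favour the test arms.* If losses fell mainly on glimepiride they would weaken the superiority contrast. The SAP does not show which arm they would fall on.

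**Conclusion.** The point holds in two limited respects. By the SAP's own cut-offs, a major event above 50 and below 54 mg/dL is a non-event at step 2 and does not prevent success in the composite. And the step 2 test excludes dosed patients for lacking a value that the endpoint does not need.

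The effect is probably small and its size is not known from the SAP. The allowance of 15 to 16 patients per arm is an upper guide, and the band is three whole mg/dL values wide. It would affect the conclusion only if confirmed events are sparse, as in the assumed 10 vs 2 case, and the direction is open. The change is still worth making, because it uses data already collected, removes a post-randomisation exclusion and brings the endpoint into line with the SAP's own severity categories.

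**What to change.** 1. **Population (2.3, 4.8.2, Table 11).** Run the hypoglycaemia-only endpoints (3.2 item 1, and the any-hypoglycaemia and symptomatic ≤70 mg/dL endpoints in 3.3) in all randomised patients with at least one dose, by randomised arm. Keep the same logistic model with baseline HbA1c. Name the set explicitly, since 2.5 assigns patients by treatment received.
2. **Definition (3.2, 4.3, 4.3.1, 3.3).** Count confirmed or major events, as 4.9.6 already defines them, at step 2 and in the composite. Keep the ≤50 mg/dL-only version as supportive. Section 5 lists no change from the protocol for this endpoint; if the protocol fixes its definition, leave step 2 as it is and prespecify confirmed or major as a sensitivity analysis.
3. **Wording.** Reconcile the bracket in 1.1.3 with 3.2, 3.3 and 4.9.6.
4. **Assisted events without a reading.** Show them as their own line in the hypoglycaemia summaries. Do not add assisted events to the endpoint without a glucose limit, because that would admit events at normal glucose.

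The cost is a small change of definition and wording plus one supportive table, settled before unblinding, with no new data. The downside is that the headline definition differs slightly from a pure ≤50 mg/dL one.

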1.1.2 Secondary objectives

- To compare the proportion of patients reporting confirmed hypoglycaemia episodes during the 52-week treatment period between dapagliflozin plus metformin and dapagliflozin plus saxagliptin plus metformin with glimepiride plus metformin
- To compare the change from baseline in total body weight at week 52 between dapagliflozin plus metformin and dapagliflozin plus saxagliptin plus metformin with glimepiride plus metformin
- To compare the change from baseline in FPG at week 52 between dapagliflozin plus metformin and dapagliflozin plus saxagliptin plus metformin with glimepiride plus metformin
- To compare the time to rescue treatment among the treatment groups during the 52 week treatment period between dapagliflozin plus metformin and dapagliflozin plus saxagliptin plus metformin with glimepiride plus metformin

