4.3 Secondary analysis

Four key secondary endpoints have been identified:

- 1. Proportion of patients reporting at least 1 episode of confirmed hypoglycaemia (symptomatic + blood glucose ≤50 mg/dL) during the double-blind treatment period
- 2. Change in total body weight from baseline to week 52
- 3. Change in FPG from baseline to week 52
- 4. Time to rescue during the 52 week treatment period

The hypotheses of the above four key secondary endpoints will test for superiority of dapagliflozin and dapagliflozin plus saxagliptin over glimepiride when used as add-on therapy to metformin - where superiority implies smaller proportions of patients experiencing at least one episode of hypoglycaemia, greater reductions in body weight and FPG; and a longer time to rescue treatment.

A superiority test of the dapagliflozin plus saxagliptin added to metformin group versus the glimepiride added to metformin group will also be conducted for the primary efficacy variable of change in HbA1c from baseline to week 52.

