4.3.1 Control of Type I error

The experiment-wise type I error will be controlled to a maximum of 5%. A hierarchical closed testing procedure will be employed such that key secondary endpoints will be considered for statistical significance (in terms of superiority) only if non-inferiority of the primary endpoint is concluded and that a key secondary endpoint will be considered for statistical significance only if the test ordered before it is found to be statistically significant. At each step, dapagliflozin plus saxagliptin added to metformin versus glimepiride added to metformin will be tested first followed by the test for dapagliflozin added to metformin versus glimepiride added to metformin except for the superiority tests of the primary endpoint and the endpoint of total body weight. The test of superiority for HbA1c will include only the comparison of dapagliflozin plus saxagliptin added to metformin versus glimepiride added to metformin. For total body weight, dapagliflozin added to metformin versus glimepiride will

be tested first followed by dapagliflozin plus saxagliptin added to metformin versus glimepiride added to metformin.

The following testing order will be followed for the overall type I error control:

- 1. Change from baseline in HbA1c at Week 52 (test for non-inferiority)
- 2. Proportion of patients reporting at least 1 episode of confirmed hypoglycaemia at Week 52 (test for superiority)
- 3. Change in total body weight from baseline to Week 52 (test for superiority)
- 4. Change from baseline in HbA1c at Week 52 (test for superiority of dapagliflozin plus saxagliptin added to metformin vs glimepiride added to metformin only)
- 5. Change in FPG from baseline to Week 52 (test for superiority)
- 6. Time to rescue at Week 52 (test for superiority)

The statistical comparisons will be done using a comparison-wise type I error of 5% (2-sided). For all other secondary variables and exploratory variables, nominal p-values will be reported without multiplicity controlled significance testing.

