4.5.6 Kaplan-Meier curve and estimates for time-to-event analysis

Kaplan-Meier plots of time to rescue will be displayed by treatment group. Unless otherwise specified, the plot will be presented only when there are at least 5 events in one treatment group. Additionally, a table will accompany the plot and will display the Kaplan-Meier estimates of the cumulative proportion (with 95% confidence interval based on Greenwood's method when applicable) of patients with event at specific time points by treatment group. If the estimated lower bound of 95% confidence interval is below 0 or the estimated upper bound of 95% confidence interval is over 1, then it will be restricted to 0 or 1 respectively.

Time to rescue is defined as the time (in days) from the first dose date after randomisation to the date at which the patient first meets the following rescue criterion: (which is confirmed),

- i. FPG > 240 mg/dL (13.3 mmol/L) for the period after Visit 2 to and including Visit 8 (Week 0 to 12) OR
- ii. FPG > 200 mg/dL (11.1 mmol/L) for the period after Visit 8 to and including day of Visit 9 (Week 12 to 24) OR
- iii. HbA1c > 8% for the period after Visit 9 to and including Visit 12 (Week 24 to 52)

Time to rescue will be censored at the earliest of discontinuation of study medication/study, or study completion, or time of insulin start (for those subjects who received rescue treatment without confirmed rescue criteria).

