dapagliflozin added to metformin and dapagliflozin plus saxagliptin added to metformin compared to glimepiride added to metformin.

The time spent below HbA1C target (<7% and <7.5%) from baseline to week 52 will be analysed using an analysis of covariance (ANCOVA) model with fixed effects for treatment group and baseline HbA1c (see section 4.5.5). The change from baseline at week 52 in a) BMI and b) waist circumference will be analysed using an ANCOVA model with fixed effects for treatment groups and respective baseline covariates (see section 4.5.5). LOCF will be applied as detailed in section 4.6.2 for the latter two analyses. The ANCOVA model will be used to derive a least squares estimate of each test drug combination versus the control with 95% CI and (a corresponding 2-sided) p-value. In addition, a 2-sided 95% CI for the mean change within each treatment group will be calculated.

Time to rescue will be analysed using a Cox proportional hazards model with the Efron method (Ref 2) for handling ties (i.e., same rescue times). Estimates of the hazard ratio and 95% CI will be provided. Kaplan-Meier estimates will be calculated and plotted by treatment group. Median time to rescue and their 95% CIs (derived from the Kaplan-Meier estimates) will also be reported. Patients will be censored at the final visit (Visit 12; week 52) if rescue has not occurred by then (Section 4.5.6), or will be censored at the time of insulin start (for those subjects who received rescue treatment without confirmed rescue criteria). The proportional hazards (PH) assumption of the Cox model will be visually checked (e.g., the survival curves should not cross for the PH to hold). If the PH assumption is not met, the time to rescue will be analysed using a Wilcoxon test (using SAS proc lifetest).

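### Time to rescue, the last step with type I error control, has two incompatible event definitions in SAP 3.2 and 4.5.6

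*SAP*

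**What the plan says.** - **SAP 3.2** lists the fourth key secondary variable as "Time to rescue (start of insulin or discontinuation due to lack of glycaemic control) during the 52-week double-blind treatment period", and sends the reader to 4.5.6 for the calculation.
- **SAP 4.5.6** runs the clock from first dose "to the date at which the patient first meets the following rescue criterion". The criterion must be confirmed: FPG above 240 mg/dL up to week 12, FPG above 200 mg/dL from week 12 to 24, HbA1c above 8% from week 24 to 52. On censoring it says "Time to rescue will be censored at the earliest of discontinuation of study medication/study, or study completion, or time of insulin start", with insulin start applying to patients rescued without confirmed criteria. Discontinuation for lack of glycaemic control is not excepted.
- **SAP 4.8.2** specifies the Cox model and says "Patients will be censored at the final visit (Visit 12; week 52) if rescue has not occurred by then", citing 4.5.6, "or will be censored at the time of insulin start (for those subjects who received rescue treatment without confirmed rescue criteria").
- **SAP 1.1.2 and 4.3** frame the question around treatment: "To compare the time to rescue treatment among the treatment groups during the 52 week treatment period", with superiority meaning, among other things, greater reductions in weight and FPG "and a longer time to rescue treatment".
- **SAP 4.3.1** places the endpoint sixth and last in the controlled order: "Time to rescue at Week 52 (test for superiority").

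**The concern.** Section 3.2 names two events: insulin start and a lack-of-control stop. The section it cites counts neither. It counts a laboratory finding, and it turns both named events into censoring when no confirmed criterion came first. The cross-reference therefore does not settle the matter.

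The endpoint belongs to the hierarchy that controls the experiment-wise error at 5%. A controlled test needs its event, event date and censoring fixed before unblinding. Here two analysts could each follow the SAP and obtain different event sets. SAP 4.4 restricts sensitivity analyses to the primary endpoint, so no planned analysis would show the effect of the choice. Patients who stop for lack of control are plausibly close to failure, so censoring them may also be informative.

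**Working it through.** **1. Place in the hierarchy (SAP 4.3.1).** Steps 1, 2, 3 and 5 each hold two comparisons and step 4 holds one: 2 + 2 + 2 + 1 + 2 = 9. Step 6 adds two, making 11. Time to rescue is reached only after nine successes.

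**2. The two rules side by side.**

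| Patient | SAP 3.2 | SAP 4.5.6 |
|---|---|---|
| (a) Stops for lack of control, no earlier confirmed criterion | Event | Censored |
| (b) Insulin rescue, no confirmed criterion | Event | Censored |
| (c) Confirmed criterion, then neither insulin nor a lack-of-control stop | No event | Event |
| (d) Confirmed criterion, then insulin | Event at insulin start | Event at criterion date |

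The SAP makes (b) and (c) possible. For (b), Table 10 (4.7.3.1) treats insulin given in a hospital stay for glycaemic control as rescue. For (c), the rescue text in 1.2.4.2 has glimepiride/placebo up-titrated first in patients below their maximum tolerated dose, and 4.5.6 accepts criteria up to and including Visit 12. The temporary insulin allowed in Table 10 is a further loose end: read literally it is a start of insulin in 3.2, but 4.5.6 censors only insulin given as rescue.

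**3. The SAP's own figures.** It gives no event count, rescue rate or hazard ratio for this endpoint, so there is nothing to reproduce. All rates below are assumptions; 290 per arm is the evaluable number in SAP 1.3.

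**4. Equal rates in both arms.** Model: independent exponential times over 364 days to confirmed criterion, unconfirmed insulin, lack-of-control stop and other dropout (12%), with insulin within 28 days of the criterion. Assumed: 10–30% meet a criterion by week 52; (a) and (b) 1–2% each; (c) 10–20% of those meeting a criterion. The hazard ratio is 1.00 under both rules, yet about 9 to 27 of 290 patients per arm change event status. In the middle case (20% meet a criterion, (a) and (b) 2%, (c) 15%) the event totals are 53 under one rule and 54 under the other, but 19 patients change status. Similar totals can hide the difference.

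**5. Unequal rates, one group at a time.** Here insulin starts at the criterion date and the other groups are zero. Cumulative hazard is H = −ln(1 − p), and the hazard ratio is the ratio of summed hazards, test over glimepiride. With equal criterion rates the 4.5.6 hazard ratio stays 1.00. Under 3.2:

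- (a) 2% v 6%. Criterion 10%: (0.1054 + 0.0202)/(0.1054 + 0.0619) = 0.75. Criterion 30%: (0.3567 + 0.0202)/(0.3567 + 0.0619) = 0.90. Reversed: 1.11 to 1.33.
- (b) 2% v 4%. Criterion 10%: 0.1256/0.1462 = 0.86. Criterion 30%: 0.3769/0.3975 = 0.95. Reversed: 1.05 to 1.16.
- (c) 10% v 30% of those meeting a criterion: 1.29 to 1.33 by simulated Cox model (800,000 per arm, Monte Carlo error about 0.01). Reversed: 0.75 to 0.78.

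**6. Change of direction.**

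- Criterion met by 18% v 20%, with (c) 10% v 30%. Under 4.5.6: 0.1985/0.2231 = 0.89. Under 3.2 the proportions going on to insulin are 0.18 × 0.90 = 16.2% and 0.20 × 0.70 = 14.0%, so ln(0.838)/ln(0.860) = 1.17.
- Criterion met by 22% v 20%, with (a) 2% v 6%. Under 4.5.6: 0.2485/0.2231 = 1.11. Under 3.2: (0.2485 + 0.0202)/(0.2231 + 0.0619) = 0.94.

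**7. Effect on power.** Assume 8% v 14% with both criterion and insulin, 6% v 2% with a criterion only, and 2% v 4% with insulin or a lack-of-control stop only. Section 3.2 then counts 10% v 18%: hazard ratio ln(0.90)/ln(0.82) = 0.53, power 81% (Schoenfeld formula, 290 per arm). Section 4.5.6 counts 14% v 16%: ln(0.86)/ln(0.84) = 0.87, power 10%. Other splits favour 4.5.6 instead.

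**The case against.** The strongest reply is that 3.2 defers to 4.5.6. Only 4.5.6 gives a time origin, an event date and a censoring list, and 4.8.2 cites it and repeats its insulin censoring. Section 3.2 cannot be programmed alone, so a programmer would probably follow 4.5.6, and the fault may be no more than an unaligned parenthesis. That is a fair forecast of what would be programmed. It does not remove the conflict: a calculation should implement the definition it serves, and this one censors the events that the definition names. The objective and the hypothesis also speak of rescue treatment, which is nearer to 3.2.

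Several side points carry little weight. The failure of 4.8.2 to list discontinuation is not a third version, because it cites 4.5.6. How a criterion is confirmed may properly be left to the protocol; its absence here means only that the size of group (c) cannot be judged. Temporary insulin is a problem only on a literal reading of 3.2.

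It is also true that the hazard ratios away from 1.00 rest on assumed two- to threefold arm imbalances, for which the SAP offers no support. They show what can happen, not what is likely. One mechanism could make group (c) differ by arm: up-titration delivers active drug in the glimepiride arm and placebo in the others. That is an inference and not a figure from the SAP.

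**Conclusion.** The concern holds. For an endpoint under type I error control, the SAP states two event definitions that classify the same patients differently, and no other section resolves this. They agree only if every confirmed criterion leads to insulin or a lack-of-control stop, every such event follows a confirmed criterion, and the dates match.

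The consequence is narrow: it touches the two comparisons of step 6 and nothing before them. Its size in this trial is unknown. The illustrations assume the rates and the arm imbalances and treat event times as independent; they show reclassification only and do not measure informative censoring. This should be fixed, but it does not threaten the primary conclusion.

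**What to change.** Before unblinding, amend 3.2, 4.5.6 and 4.8.2 so that the confirmatory test has one event definition, one event date and one censoring rule. State how the analysis classifies:

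- discontinuation for lack of control with no earlier confirmed criterion;
- insulin rescue without a confirmed criterion;
- a confirmed criterion without insulin;
- the temporary insulin use in Table 10.

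Pre-specify the other definition as a supportive analysis. If lack-of-control stops remain censored in the main test, do not assume that this censoring is non-informative. The supportive analysis addresses it by counting those stops as events, but it changes the other groups and the dates as well; a run that changes only those stops would isolate the effect.

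The cost is SAP wording and programming. The insulin dates, discontinuation reasons and laboratory dates are already needed by the SAP's own definitions. The clinical rescue criteria are not touched.
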